Aim 1: In the first step our multidisciplinary team will propose modifications to the general 3RP to address the needs of patients with chronic pain reported in the literature, with a focus on improving physical activity and function (see Figure , Table 1). Based on this information, we will develop a semi-structured qualitative interview script.

Hypotheses: NA

Aim 2: In the second step we will use the semi-structured qualitative interview to guide focus groups (30 total) to gather feedback on the intervention components, gauge treatment needs and expectations, as well as barriers and ways to facilitate participation in the intervention and adherence to the use of DMD and 3RP specific practice, among chronic pain patients. Participants will also be given an exit interview to answer questions that they might not feel comfortable discussing during the group setting (e.g., triangulation).

Hypotheses: NA

Specific aims for phase II are:

Aim 3: In the first step, we will pilot the adapted p3RP-DMD and p3RP programs in two initial groups (N=10/group, 20 total) of chronic pain patients and assess preliminary credibility, acceptability, satisfaction of treatment, feasibility (of recruitment and instruments) and adherence to the use of the DMD and to p3RP-specific homework.

Hypotheses: N/A

Aim 4: In the second step, we will conduct a semi-structured comprehensive qualitative exit interview at the end of the groups focused on discussing patients' perception of the rationale for and helpfulness of each individual p3RP specific module, patients' perception of the rationale and helpfulness of using the DMD in increasing physical activity/function, patients' perception of the importance and ease of adherence to DMD and adherence to p3RP specific homework, and patients' burden of questionnaire completion.

Hypotheses: N/A

Specific aims for phase III are:

Aim 5: We will conduct an RCT (N = 80 chronic pain patients, 40/arm, 8 groups total, accounting for 25% attrition) of the newly refined p3RP-DMD versus the newly refined p3RP. We will compare the credibility, acceptability, adherence, satisfaction with treatment, feasibility (of recruitment, refined intervention, study procedures, and instruments) between the two interventions.

Hypotheses: N/A

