During enrollment, participants have the option to consent to receiving reminders in the form of phone calls, text messages, or email over the course of the intervention, depending on personal preference. Between-session contact will be used with the goal of increasing treatment adherence and engagement. Participants may opt-out of the text message contact option at any point.

After enrollment, participants will be assigned to one of the two intervention groups using a randomized block design to ensure that equal numbers of patients are split into the p3RP-DMD and p3RP groups. To prevent participant unblinding, participants will be asked not to share specific information discussed in the group (e.g., skills learned, topics discussed) on social media sites (e.g., Facebook groups or internet chat groups) or with other acquaintances for the duration of the study. The groups will be conducted in person at MGH by trained study therapists over 12 weeks and include 10 active intervention sessions. Each session will last approximately 90 minutes. Participants will also be asked to answer follow-up assessment questionnaires 3 months following program completion. These questionnaires will be administered over the phone for 30-45 minutes.

Participants will complete demographics assessments at baseline, in addition to psychological/behavioral assessments and a 6-minute walk test at both baseline and post-test timepoints. Participants in the p3RP-DMD group will pair their Fitbit DMD to a smartphone with Bluetooth, and the Fitbit will inform an individualized quota-based behavioral plan to improve both adherence and efficacy. All participants will also wear an accelerometer for 7 days before the first treatment session (baseline) and for 7 days after the final treatment session (post-test). After each assessment week, participants will return the accelerometers in addition to a wear time log.

The following measures will be administered at all timepoints unless otherwise stated. Questionnaires at 3-month follow-up will be administered over the phone.

Demographics – *baseline only*

Credibility and Expectancy Questionnaire (CEQ) – *baseline only*

Pittsburgh Sleep Quality Index (PSQI)

PROMIS Physical Function SF

Physical Activity Scale for Individuals with Physical Disabilities (PASIPD)

WHO Disability Assessment Scale (WHODAS) 2.0

Numerical Rating Scale for Pain (NRS)

Pain Resilience Scale (PRS)

PROMIS Anxiety SF

PROMIS Depression SF

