PROMIS Social Isolation SF

PROMIS Emotional Support SF

Measure of Current Status (MOCS)

Pain Catastrophizing Scale (PCS)

Tampa Kinesiophobia Scale

Cognitive and Affective Mindfulness Scale (CAMS-R)

Patient Global Impression of Change (PGIC) – *post-test and 3-month follow-up only*

Client Satisfaction Questionnaire (CSQ-3) – *post-test and 3-month follow-up only*

Participants will be given the option to complete a maximum of two make-up sessions via the Vidyo teleconferencing software. Vidyo is a HIPAA approved, secure web platform used in clinical care for patients at MGH. Participants will have a Vidyo meeting with study staff to ensure that they are comfortable using Vidyo for make-up sessions only. Ratings of patient satisfaction are high, and there have been no complaints of technological difficulties. Participants will be compensated \$20 for each of three assessments completed and \$10 for transportation (for each group session attended). They can also receive up to two additional \$25 payments for completing 6 group sessions and 8 group sessions. The maximum compensation per participant is \$230.

At study enrollment completion (e.g., no longer recruiting or enrolling, and only completing follow-up measures and data analysis), we will conduct 12 qualitative exit interviews with participants who have completed all study measures (e.g., completing questionnaires at both baseline and post-test and wearing the accelerometer at both baseline and post-test). Participants will be randomly selected to complete the interview, which will last 15 minutes and will be completed over the phone with the study clinician. We will conduct qualitative exit interviews within the following four categories: 1) 3 participants who were sedentary at baseline (i.e., less than 5,000 steps) and increased their step-count at post-test; 2) 3 participants who were sedentary and did not increase their step-count at post-test; 3) 3 participants who were not sedentary at baseline and did increase their step-count; 4) 3 participants who were not sedentary at baseline and did not increase their step-count at post-test. Participants will be called and will be contacted until clinician is able to speak to participant. If a participant declines, a new random participant number will be selected.

VI. BIOSTATISTIC ANALYSIS

Phase I

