Patients will be informed that there are no foreseeable physical risks from this research study. They will be informed that in the unlikely situation that they might feel uncomfortable with the topic of discussing within the group, they can alert the group leader who will provide help, as needed.

As Vidyo is HIPAA approved and secure, there are no risks associated with its use. However, participants will be asked to ensure that they are in a private room during the group sessions, to protect their privacy and that of group members. As with any group studies, there may be confidentiality issues, but we will discuss the importance of maintaining confidentiality at the beginning of each group.

VIII. POTENTIAL BENEFITS

Patients will be informed that there may be no direct benefit from participating in this research study. Some patients may become more physically active, more resilient, better able to cope with pain and stress, and experience a better quality of life.

In the future, knowledge from this research may benefit others by providing information on how to better mind body interventions for patients with chronic pain.

IX. MONITORING AND QUALITY ASSURANCE

Phase I: The focus groups will be conducted uniformly using a semi structured interview script that will be finalized during the first few months of the study. The Principal Investigator will be responsible for ensuring compliance with IRB procedures.

Phase II: Study therapists will have weekly team meetings and clinical supervision. Study staff will follow the patient manuals for each group and assure that all items on all questionnaires have been addressed. Once completed, data will be checked for out of range values using frequency distributions prior to analyzing the data. The Principal Investigator will be responsible for ensuring compliance with IRB procedures.

Phase III: Feasibility will be assessed as depicted in the prior section. We will calculate the proportion of patients who complete at least 6 of the 8-planned treatment sessions (75%), along with the 95% confidence interval (CI) around this discontinuation rate. Treatments are considered feasible if over 70% of participants complete at least 6 treatment sessions.

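### The Phase III feasibility criterion counts 6 of 8 sessions although Phase III has 10 active sessions; separately, its one planned 95% CI makes no allowance for the 8 therapy groups, which matters only if the ICC is about 0.05 or more

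*Combined protocol and SAP*

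**What the plan says.** Section IX, Phase III, defines the feasibility measure as the "proportion of patients who complete at least 6 of the 8-planned treatment sessions", gives 75% in brackets, and adds a 95% CI "along with the 95% confidence interval (CI) around this discontinuation rate". The decision rule follows: "Treatments are considered feasible if over 70% of participants complete at least 6 treatment sessions".

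Section V, Phase III, describes a different programme length: "The groups will be conducted in person at MGH by trained study therapists over 12 weeks and include 10 active intervention sessions".

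Section II, Aim 5, sets the size and structure: "N = 80 chronic pain patients, 40/arm, 8 groups total, accounting for 25% attrition". It then states the purpose: "We will compare the credibility, acceptability, adherence, satisfaction with treatment, feasibility" between the two interventions. No quantitative method is given for that comparison, and the hypotheses entry reads N/A.

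Section VI covers qualitative coding and the handling of Fitbit data. Neither Section VI nor Section IX names a CI method or mentions a group effect, an ICC or a design effect. Neither says whether the completion proportion is pooled or per arm.

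**The concern.** There are two separate problems in the same short passage.

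The first is definition. The criterion is written against 8 sessions and the Phase III procedures against 10. A participant who attends 6 sessions has had three quarters of the programme on one count and three fifths on the other. The quantity is also called completion in one clause and discontinuation in the next. A reader of the results could not tell what the proportion, or its interval, refers to.

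The second is precision. The outcome is attendance at group meetings. Members of a group share a timetable, a leader and peers, so their attendance may be correlated. An interval that treats 80 people as independent is then too narrow. This is the only precision statement attached to the feasibility measure, in a pilot intended to prepare a large RCT.

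**Working it through.** **Session count**

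- Section IX: 6/8 = 75%, which reproduces the bracketed figure.
- Section V: 6/10 = 60%.
- If the intended bar is 75% of sessions, then 0.75 × 10 = 7.5, which means 8 whole sessions. Someone who attends 6 or 7 of 10 counts as a completer on one reading and not on the other.
- The payment ceiling in Section V does not settle it. Three assessments at \$20 and two payments of \$25 make \$110. The remaining \$230 − \$110 = \$120 is 12 transport payments of \$10, each tied to a group session attended. That matches neither 8 nor 10.

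**Group structure**, from Aim 5: 2 × 40 = 80; 80/8 = 10 per group; 40/10 = 4 groups per arm.

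**Assumptions not in the documents:** ICC of 0.01, 0.02, 0.05 or 0.10; true completion 75%; equal groups of 10; an ordinary binomial interval.

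**Formulas**

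- Design effect: DE = 1 + (10 − 1) × ICC.
- Approximate coverage of a nominal 95% interval: 2Φ(1.96/√DE) − 1.
- Half-width allowing for group: 1.96 × √(0.75 × 0.25 × DE/n).

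Example at ICC 0.05, pooled: DE = 1 + 9 × 0.05 = 1.45; half-width = 1.96 × √(0.1875 × 1.45/80) = 11.4 points.

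| ICC | DE | Coverage by formula | Half-width, n = 80 | Half-width, n = 40 |
|---|---|---|---|---|
| 0 | 1.00 | 95.0% | 9.5 | 13.4 |
| 0.01 | 1.09 | 94.0% | 9.9 | 14.0 |
| 0.02 | 1.18 | 92.9% | 10.3 | 14.6 |
| 0.05 | 1.45 | 89.6% | 11.4 | 16.2 |
| 0.10 | 1.90 | 84.5% | 13.1 | 18.5 |

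The formula ignores the choice of CI method. Exact coverage under a beta-binomial model at 75% completion is:

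| ICC | Pooled, 8 groups: Wald / Wilson / Clopper-Pearson | Per arm, 4 groups: Clopper-Pearson |
|---|---|---|
| 0 | 94.1 / 94.8 / 96.1% | 97.2% |
| 0.01 | 93.0 / 93.8 / 95.2% | 96.5% |
| 0.02 | 91.9 / 92.7 / 94.3% | 95.7% |
| 0.05 | 88.4 / 89.4 / 91.3% | 93.2% |
| 0.10 | 83.0 / 84.1 / 86.5% | 88.7% |

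Completion and discontinuation are complements, so these figures are the same whichever is reported. If the 25% attrition is removed first (60 people, 7.5 per group), formula coverage is about 94% at ICC 0.01 and 87% at 0.10. Completion is more naturally counted over everyone enrolled, so 10 per group is the base used here.

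**Interval allowing for group.** With 8 groups in 2 arms there are 6 df, and t = 2.447. The pooled half-width is 2.447 × √(0.1875 × DE/80) = 11.8, 14.3 and 16.3 points at ICC 0, 0.05 and 0.10. Simulated coverage is 94.3%, 94.1% and 93.6%. Per arm, with 3 df and t = 3.182, the half-width is 21.8, 26.2 and 30.0 points, too wide to be useful.

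**The case against.** On session count, the decision rule can be applied as written: it asks for at least 6 sessions and needs no denominator. That is fair, but the sentence defining the measure ties the 6 to 8 planned sessions and to 75%, so what the rule was meant to require in a 10-session programme is still unclear.

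On clustering, most of the opposing case stands.

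- The ICC is assumed, and parts of the design act on individuals and may keep it low. "Participants will be given the option to complete a maximum of two make-up sessions", payment is per session attended, and participants may opt for "receiving reminders in the form of phone calls, text messages, or email over the course of the intervention".
- At low ICC the choice of CI method matters at least as much as grouping. Clopper-Pearson still covers about 95% pooled at 0.01, and 93.2% per arm at 0.05.
- The 6-df interval costs about 25% in width (2.447/1.96 = 1.25) even if there is no group effect.

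What survives is that at ICC 0.10 every ordinary method falls short, whether pooled or per arm.

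Three stronger readings are tempting, and the documents do not support them.

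- A reader might infer that the planned interval covers only about 85%. That needs an ICC of 0.10 and a binomial method, neither of which the documents state.
- A reader might infer that the feasibility decision is compromised by clustering. The rule compares the observed proportion with 70% and does not use the interval.
- A reader might infer that the Aim 5 comparison has an inflated type I error. A simulated unadjusted test of completion between arms does reject in 6.0%, 7.2%, 10.4% and 15.8% of null trials at ICC 0.01, 0.02, 0.05 and 0.10, but no such test is planned.

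**Conclusion.** The session-count conflict is real, needs no assumption, and is the more important of the two. Sections V and IX give 10 and 8 sessions for the same phase, so the cut-off of 6 means 60% or 75%, and the measure is labelled both completion and discontinuation. The documents do not show which count is intended.

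The missing allowance for group is a minor point. It is negligible at an ICC of about 0.01 and becomes material only at about 0.05 or more, where pooled coverage at 75% completion falls to 88% to 91%, and to 83% to 86% at 0.10. This rests on assumed ICCs, equal groups of 10 and an ordinary binomial method. It affects only the precision reported, not the feasibility call.

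**What to change.** 1. Reconcile Sections V and IX on the number of sessions to which the feasibility cut-off refers. State that the proportion and its CI are for completion, and whether they are pooled or per arm.
2. Report completion for each of the 8 groups and name the CI method. For a pooled figure, use a cluster-adjusted interval with a t reference on 6 df. Per arm, with only 4 groups, use a Clopper-Pearson interval and show beside it the width at assumed ICCs of 0.05 and 0.10 (at 75% completion, 16.2 and 18.5 points by formula, against 13.4 with no group effect).
3. Report Aim 5 descriptively by arm. Only if a difference arising after sessions begin is given a CI or test, allow for group with a small-sample correction, for example 4 versus 4 group means with t on 6 df.

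The cost is wording and a little analysis, using each participant's group identifier and no new assessments. The price is wider intervals: pooled, about 12 points at ICC 0 and 14 at ICC 0.05, against 9.5 unadjusted.

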3.1 Procedures Overview

The present proposal aims to adapt, pilot and examine the credibility, acceptability, adherence and feasibility of the 3RP adapted for chronic pain (p3RP), and the p3RP-DMD, which is the pain specific 3RP integrated with a commercial digital monitoring device (DMD), the Fitbit. This R34 feasibility project will lay the groundwork for a large RCT of the p3RP-DMD vs p3RP vs pHEP attention placebo control, and will help understand whether the DMD Fitbit is

necessary to comprehensively improve function. Consistent with prior theory within a subsequent R01 we will test the hypothesis that the p3RP-DMD will be superior to the p3RP and pHEP in improving and sustaining improvements in

objective, performance based and self-reported physical and emotional function in patients with heterogeneous chronic pain. Using the specific NCCIH R34 mechanism we now follow an iterative design^{82,83} to adapt the general 3RP and refine both the p3RP and the integrated p3RP-DMD interventions to maximize feasibility, acceptability, credibility, recruitment protocol, adherence and measurements for patients with heterogeneous chronic pain. To allow objective measurement of activity in both p3RP and p3RP-DMD groups, we will use Accelerometer DMDs for 1 week at baseline and post-test. The Fitbit DMD will be used to address/reinforce activity consistent with an individualized pacing plan, and to assess daily activity during the program only for those randomized to the p3RP-DMD.

During the RCT phase, participants will be randomized 1:1 to p3RP-DMD or p3RP using block randomization. The study team will be blinded and the program manager, not involved in the study, will be responsible for assigning numbers to each participant. Participants will not know whether they are assigned to the p3RP-DMD intervention or the p3RP control. Rather, they will be informed that they will be randomized to one of 2 physical activity groups, in an effort to identify which one works best in patients with chronic pain. In order to prevent unblinding, participants will be asked to not share information discussed in the group on social media sites (e.g., Facebook groups or internet chat groups) or with other acquaintances for the duration of the study. We will also explain to study participants how sharing of information would potentially negatively impact the validity of study results.

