Aim 6: By the end of this trial we aim to have two interventions (p3RP-DMD and p3RP) with high credibility, acceptability and feasibility, a recruitment, retention plan and study procedures protocol to ensure minimal random error, and outcome measures sensitive to change.

Hypotheses: N/A

Aim 7: At the end of study enrollment (e.g., no longer recruiting or enrolling participants and only conducting follow-ups with participants and conducting data analysis), we will conduct semi-structured qualitative interviews (12 total) once participants have completed all study procedures (e.g., completing both baseline and post-test questionnaires and wearing the accelerometer at both time points). This interview will be used to inform the future development of the program and to understand ways to better improve physical activity and discuss participants perceptions of the accelerometer.

Hypotheses: N/A

III. SUBJECT SELECTION

Subjects will be adult new patients presenting to Partners-affiliated medical practices (e.g., the Pain Clinic at Massachusetts General Hospital, the Spine Center at Massachusetts General Hospital, Brigham and Women's Hospital Anesthesia and Pain Management Center, and Spaulding Rehabilitation Hospital's outpatient center), and Boston area pain centers and medical practices that treat chronic pain patients. The MGH Center for Pain Medicine sees approximately 15,000 patient visits yearly. The main diagnoses are: chronic low back pain and fibromyalgia. Inclusion and exclusion criteria were selected following guidelines for psychosocial treatment development 82-83 (see Table 1. Above).

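### The 70% session-completion rule for Phase III is not applied to each arm; read literally, one pooled proportion decides feasibility for both interventions

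*Combined protocol and SAP*

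**What the plan says.** The Phase III paragraph of Section IX plans a single proportion: the share of patients attending six or more of eight sessions, which it equates with 75%. The interval is described as "along with the 95% confidence interval (CI) around this discontinuation rate". The verdict follows: "Treatments are considered feasible if over 70% of participants complete at least 6 treatment sessions". Neither sentence mentions an arm or a denominator. The paragraph refers back to an earlier section for the feasibility method, but no earlier section gives a completion calculation or an arm-level rule. Section VI covers only qualitative coding and the handling of Fitbit data.

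Two aims in Section II depend on this verdict. Aim 5 plans to compare, among other things, "feasibility (of recruitment, refined intervention, study procedures, and instruments) between the two interventions". Aim 6 states the goal: "we aim to have two interventions (p3RP-DMD and p3RP) with high credibility, acceptability and feasibility". Section 3.1 says that "participants will be randomized 1:1 to p3RP-DMD or p3RP using block randomization", and Aim 5 gives 80 patients, 40 per arm, in 8 treatment groups, allowing for 25% attrition.

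**The concern.** The aims ask a question about each intervention; the rule as worded answers one about the trial population. If the arms are combined, good attendance in one can carry poor attendance in the other, and both are labelled feasible. Because the unit is not stated, two analysts could also reach opposite verdicts from the same data without departing from the text.

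The wording leans towards pooling: the proportion, the interval and the verdict are each given once. A little further on in Section IX, the paragraph on accelerometer and Fitbit adherence does say which groups each summary covers, so the omission here is noticeable. What is at stake is whether the feasibility conclusion of this pilot supports what Aim 6 wants to claim for p3RP-DMD and p3RP separately.

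**Working it through.** **Inputs from the documents.** N = 80, 40 per arm, 1:1 (Aim 5; Section 3.1). Criterion: strictly more than 70% (Section IX).

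**Assumptions.** The denominator is everyone randomised. Participants are independent, so clustering by treatment group is ignored. True completion rates are not in the documents and are shown as a range.

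**The plan's own figure.** 6/8 = 75%, as stated. The 70% threshold has no derivation to reproduce.

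**Counts needed.**
- Pooled: 0.70 × 80 = 56, so at least 57/80 (71.25%).
- Per arm: 0.70 × 40 = 28, so at least 29/40 (72.5%).

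**What a pooled pass can contain.** 36 + 21 = 57, so 36/40 (90%) with 21/40 (52.5%) passes. The Wilson interval for 21/40, with z = 1.96:
- centre = (p + z²/2n)/(1 + z²/n) = (0.525 + 0.0480)/1.0960 = 0.523
- half-width = z√[p(1−p)/n + z²/4n²]/(1 + z²/n) = 1.96 × √(0.006234 + 0.000600)/1.0960 = 0.148
- interval = 0.375 to 0.671, all below 70%. The Clopper-Pearson interval, 36.1% to 68.5%, agrees.

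The extreme split is 40/40 with 17/40 (42.5%, Wilson 29% to 58%).

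**How often it happens.** Let X and Y be independent binomial counts with n = 40. Sum P(X = i)P(Y = j) over the cells where i + j ≥ 57, and over the subset where i or j is below 29.

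| Assumed true rates | Pooled rule passes | Passes with an arm at or below 70% | Both arms pass separately |
|---|---|---|---|
| 90% / 60% | 0.83 | 0.76 | 0.07 |
| 85% / 60% | 0.66 | 0.59 | 0.07 |
| 80% / 65% | 0.65 | 0.47 | 0.19 |
| 75% / 75% | 0.82 | 0.31 | 0.51 |
| 80% / 80% | 0.98 | 0.15 | 0.83 |

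An arm with a true rate of 60% reaches 29/40 with probability 0.071. One at 75% does so with probability 0.715, and 0.715² = 0.511 for both.

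**Precision.** At 70%, the approximate half-width is 1.96√(0.7 × 0.3/40) = 14.2 points per arm and 1.96√(0.7 × 0.3/80) = 10.0 points pooled.

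**The case against.** The strongest reply is that the plan never says the arms are combined. The noun Treatments is plural, Aim 5 compares the interventions and Aim 6 speaks of two of them, so a sensible analyst might apply 70% to each arm. On that reading none of the splits above could pass. This stands as far as it goes: pooling is the literal reading, not a stated fact. It does not remove the need for an edit, because the text supports both readings.

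The completion rates are also assumed, and large gaps between arms may not occur. A reader might infer that daily device use will depress attendance in p3RP-DMD. The documents do not support that: Sections 1.4 and 1.5 expect the Fitbit to help motivation and adherence, and eligibility requires willingness to use it daily. The calculation does not depend on which arm is weaker.

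An arm at or below 70% in the data is not proof that it is infeasible. With both arms truly at 75%, the pooled rule passes while at least one arm misses by chance with probability 0.31. That is a fair caution, and a reason to show intervals by arm.

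Two further inferences go too far. One is that the rule hides the difference between arms; Aim 5 still plans that comparison, though without a statistic or threshold. The other is that the rule alone sends an intervention into the later large trial; Section IX says only that treatments are considered feasible, and no passage makes progression depend on this number alone.

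**Conclusion.** The point holds as a gap in specification with a material consequence. The plan does not apply its 70% criterion to each arm, although Aim 6 needs each intervention to be feasible. Under the literal pooled reading, both can be declared feasible with one arm at 21/40, whose whole interval lies below 70%. At assumed true rates of 90%/60% and 85%/60%, the rule passes while the weaker arm misses 70% with probability 0.76 and 0.59. These figures rest on all 80 randomised as denominator, independence between participants and the assumed rates.

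The documents do not show that pooling was intended. Nor is every pooled pass with unequal arms a clear failure of the weaker one: at 34/40 and 23/40 the weaker arm's Wilson interval is 42% to 71%, which includes 70%, and more than half of that arm completes. This is also the only numerical feasibility criterion, not the only numerical threshold, since Section VI sets a kappa target for coding.

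**What to change.** In the Phase III paragraph of Section IX, state that completion and its 95% CI are calculated separately for p3RP-DMD and p3RP, with everyone randomised to the arm as denominator, and that the over-70% criterion applies to each arm. Report the pooled proportion as description only. With 40 per arm, each arm then needs at least 29 completers.

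The change needs no new data. It does cost precision and pass probability. Intervals widen from about ±10 to about ±14 points, ignoring clustering within treatment groups. At a true 75% in both arms, both pass with probability 0.51 instead of 0.82 pooled; at 80% in both, 0.83 instead of 0.98. The criterion also still rests on a point estimate: 29/40 passes with a Clopper-Pearson interval of 56% to 85%, so the intervals should be read beside the verdict.

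Two inconsistencies should be settled in the same edit. The count of eight sessions must be reconciled with the ten active sessions in Section V, Phase III; six sessions is 75% of eight but 60% of ten. The interval is labelled as belonging to a discontinuation rate, whereas the proportion defined is a completion rate.
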